4. ABSTRACT

Rationale and background: The Nordic countries, Denmark, Finland, and Sweden, provide a unique setting for the study of influenza vaccine effectiveness (IVE). The ubiquitous nationwide demographic and health registers, including vaccination and surveillance data, allow for large study cohorts with near real-time data availability. Seasonal influenza remains a major public health concern, particularly for vulnerable populations such as older adults and individuals at high-risk of serious influenza outcomes. While vaccination is the primary prevention strategy, its effectiveness varies across seasons, virus subtypes, and populations. Data on timely brand-specific IVE are limited.

Research question and objectives: The aim of this project is to evaluate the brand-specific effectiveness of seasonal influenza vaccines in preventing laboratory-confirmed and influenza-related outcomes during the 2024-2025 season in key target populations in Denmark, Finland, and Sweden.

Study objective:

- To provide timely estimates of brand-specific seasonal IVE against laboratory-confirmed and influenza-related outcomes for the 2024-2025 season.

Study design: Nationwide register-based cohort analyses in Denmark, Finland, and Sweden, during the study period from 1 October 2024 until the latest available date in 2025 at time of analyses (e.g., 1 March 2025). We will employ a matched cohort design, utilizing national registers to capture vaccination status, influenza outcomes, and relevant covariates. The study will focus on individuals aged 65 years and older, and adults at high risk of adverse influenza outcomes. IVE will be estimated against laboratory-confirmed influenza, influenza-like illness, hospitalization, ICU admission, and mortality.

Population: Within Denmark, Finland, and Sweden, we will include all individuals aged 65 years and above, and adults at high risk below 65 years of age, who are known residents.

Variables: The primary outcomes are laboratory-confirmed influenza (types A and B, combined and separately), influenza hospitalization, and influenza-related death. The secondary outcomes are hospitalisation for influenza-like-illness, hospitalisation for respiratory infections, ICU admission, and all cause-mortality. Covariates include demographic characteristics and comorbidities.

Data sources: Nationwide demography- and healthcare registers within each participating country.

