Treatment assignment	Randomization: Eligible individuals are randomly assigned to receive influenza vaccination with a randomly chosen vaccine brand or no vaccination 1:1	Matching: Eligible individuals who are vaccinated in each country during the study period will be matched 1:1 with individuals who have not yet received a vaccine by age (5-yr bins), sex, region of residence, and presence of comorbidities. Unvaccinated individuals are assigned the index date (date of vaccination) of the matched vaccine recipient.
Outcomes	
Primary:
 
 • Hosp. due to Influenza – Lab. conf + J09-J11 • Lab. conf. Influenza A and B (combined and separately) • Death with influenza – Lab. conf within 30 days before date of death 
Secondary:
 
 • Hosp. due to ILI – J09-J11 • Hosp. due to ARI or SARI – J09-J22 • Hosp. due to Influenza with ICU admission • All-cause mortality 	Same as for the target trials.
Follow-up	Day 14 after date of vaccination or placebo will serve as the start of follow-up until the day of an outcome event, death, emigration or end of influenza season. Controls are censored if vaccinated.	Day 14 (time zero) after date of vaccination in each matched pair (index date) will serve as the start of follow-up until the day of an outcome event, death, emigration or end of influenza season (or latest possible date of data availability). Pairs are

		censored if controls are vaccinated.
Causal contrast of interest	
 • Intention to Treat – average effect of treatment assignment in trial population • Per-Protocol Effect – average effect among those who complied with their assigned treatment. 	
 • Modified Per- Protocol Effect – average effect among vaccinated (“do those who get the seasonal influenza vaccination benefit?”)
Statistical analysis	VE estimated as 1 - Risk Ratio at week 18 since index date using cumulative incidences from the Aalen-Johansen estimator.	Same as for the target trial. Week 18 subject to change according to data availability. Change will be made before any effectiveness results are estimated.

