	Efluelda Tetra®	QIV, adjuvanted (high-dose)	Individuals in long term care facilities (nursery homes for elderly) only

Outcomes

We will estimate VE against the laboratory-confirmed influenza outcomes listed below.

Table 4. Laboratory-confirmed influenza outcomes

Variable	Country	Data source and details
Laboratory-confirmed influenza A	Denmark	Danish Microbiology Database . Defined as a laboratory-confirmed positive influenza test with a known subtype of influenza A.
	Finland	National Infectious Diseases Register . Defined as a laboratory-confirmed positive influenza test with a known subtype of influenza A.

	Sweden	Register on surveillance of notifiable communicable diseases (SmiNet). Defined as a laboratory-confirmed positive influenza test with a known subtype of influenza A.
Laboratory-confirmed influenza B	Denmark	Danish Microbiology Database. Defined as a laboratory-confirmed positive influenza B test result.
	Finland	National Infectious Diseases Register. Defined as a laboratory-confirmed positive influenza B test result.
	Sweden	Register on surveillance of notifiable communicable diseases (SmiNet). Defined as a laboratory-confirmed positive influenza B test result.
Hospitalisation due to influenza	Denmark	The National Patient Register and the Danish Microbiology Database. Defined as a hospitalization with a PCR positive test for influenza within 14 days before to 2 days after the admission date, b) inpatient contact or at least 12 hours of contact, and c) influenza-like illness relevant diagnosis code (ICD-10: J09, J10, J11)
	Finland	National Care Register for Health Care and the National Infectious Diseases Register. Defined as a hospitalization with a PCR positive test for influenza within 14 days before to 2 days after the admission date, b) inpatient contact, and c) influenza-like illness relevant diagnosis code (ICD-10: J09, J10, J11)
	Sweden	The Swedish Patient Register and the Register on surveillance of notifiable communicable diseases (SmiNet). Defined as a hospitalization with a PCR positive test for influenza within 14 days before to 2 days after the admission date, b) inpatient contact or at least 12 hours of contact, and c) influenza-like illness relevant diagnosis code (ICD-10: J09, J10, J11)

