Influenza-related death	Denmark	The Civil Registration System and the Danish Microbiology Database. Defined as (the date of) death within 30 days after PCR positive test for influenza.
	Finland	The Finnish Population Information System and the National Infectious Diseases Register. Defined as (the date of) death within 30 days after PCR positive test for influenza.
	Sweden	The Total Population Register, the Cause of Death Register, and the Swedish Patient Register and the Register on surveillance of notifiable communicable diseases (SmiNet). Defined as (the date of) death within 30 days after PCR positive test for influenza.

Furthermore, medically attended outcomes presented in Table 5 will be assessed.

Table 5. Medically attended influenza outcomes

Variable	Country	Data source and details
Influenza-like-illness	Denmark	The National Patient Register. Defined as ICD-10 diagnostic codes J09, J10 and J11 used as a primary or secondary diagnosis.
	Finland	National Care Register for Health Care. Defined as ICD-10 diagnostic codes J09, J10 and J11 used as a primary diagnosis.
	Sweden	The Swedish Patient Register. Defined as ICD-10 diagnostic codes J09, J10 and J11 used as a primary diagnosis.
Hospitalisation for acute respiratory infections (ARI) and severe acute respiratory infections (SARI)	Denmark	The National Patient Register. A hospitalised patient is a SARI patient who a) has been admitted to hospital during the study period and has not been discharged to their home or home equivalent, b) inpatient contact or at least 12 hours of contact, and c) a ARI/SARI relevant primary diagnosis code (ICD-10: J09-J22).
	Finland	National Care Register for Health Care and the National Infectious Diseases Register. A hospitalised patient is a SARI patient who a) has been admitted to hospital during the study period and has not been discharged to their home or home equivalent, b) inpatient contact or at least 12 hours of contact, and c) a ARI/SARI relevant primary diagnosis code (ICD-10: J09-J22)
	Sweden	The Swedish Patient Register and the Register on surveillance of notifiable communicable diseases (SmiNet). A hospitalised patient is a SARI patient who a) has been admitted to hospital during the study period and has not been discharged to their home or home equivalent, b) inpatient contact or at least 12 hours of contact, and c) a ARI/SARI relevant primary diagnosis code (ICD-10: J09-J22)

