The test-negative case-control (TNCC) study design is a variant of the case-control method specifically developed for evaluating VE. (48) Due to unavailability of test negatives data in Finland and Sweden, we will conduct a TNCC study on Danish data only. In this approach, cases are individuals who test positive for influenza, while controls are those who test negative. The TNCC design offers several methodological strengths. It reduces bias from healthcare-seeking behaviour, as both cases and controls sought care and allows for efficient VE estimation during the influenza season. However, the TNCC design also has important limitations. It assumes that influenza vaccine does not affect the risk of other, non-influenza respiratory infections. (48) The design may be subject to bias if cases and

controls differ in disease severity. (49) Moreover, as the use of electronic healthcare records, including register-based data, for identifying cases and controls might cause bias (e.g., misclassification), and active enrolment of study participants is ideal in the TNCC design. (50) However, this increases the cost of the TNCC studies and limits its practicality to estimate VE against rare outcomes. Since a core assumption of the TNCC design is similar healthcare seeking behaviour among those who get tested, there is potential for selection bias if testing practices vary by vaccination status or other patient characteristics.

In the Danish population of individuals who were PCR-tested for influenza during the 2024–2025 season, we will employ a TNCC design to estimate the vaccine effectiveness against influenza infections during the 2024–2025 influenza season. We will exclude negative tests within 7 days of a previous negative test and within 21 days of a subsequent positive test. All tests within 90 days of a previous positive test will be excluded as these likely represent the same episode. Individuals can contribute with a maximum of one negative PCR test, which will be selected at random.

Patients will be considered vaccinated if they received an influenza vaccine at least 14 days before the PCR sample date. Patients will be considered unvaccinated if they have not received the influenza vaccine on the PCR test date or if they have received the influenza vaccine within two weeks before the PCR test date.

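### Laboratory-confirmed influenza A, part of a primary outcome, requires a known subtype that no other influenza outcome requires and no planned analysis uses

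*Protocol*

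**What the plan says.** Protocol section 9.1, Table 1, lists among the primary outcomes "Lab. conf. Influenza A and B (combined and separately", and the abstract gives the same outcome as "laboratory-confirmed influenza (types A and B, combined and separately". The case definitions stand in section 9.3, Table 4. For influenza A, each of the three countries has the entry "Defined as a laboratory-confirmed positive influenza test with a known subtype of influenza A". For influenza B, each has "Defined as a laboratory-confirmed positive influenza B test result". Table 4 has no row for the combined outcome.

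Other parts of the plan set a different laboratory criterion:

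- Influenza hospitalisation (Table 4) is "Defined as a hospitalization with a PCR positive test for influenza within 14 days before to 2 days after the admission date", together with contact and diagnosis-code conditions but no subtype.
- Influenza-related death (Table 4) is "death within 30 days after PCR positive test for influenza".
- In the Danish test-negative analysis (section 9.8), "cases are individuals who test positive for influenza".

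The effect measure is "VE estimated as 1 - Risk Ratio at week 18 since index date". The strata listed at the end of section 9.3 are brand, age and sex. Section 12 adds comorbidity, Covid-19 status and vaccination history. Subtype appears in neither list.

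**The concern.** The subtype condition applies to one component of a primary outcome and serves no analysis in the plan. A patient with an A-positive PCR that was never subtyped can be an influenza hospitalisation or an influenza-related death, yet a non-case for laboratory-confirmed influenza. The A outcome would then depend on how often each country's laboratories subtype, as well as on how often people are infected.

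Three things are at stake. Precision for A falls, in a study whose section 9.9 already warns of limited power for less-used brands. The weighting of A and B in the combined outcome may shift, and by different amounts in different countries, which would feed artificial heterogeneity into the random-effects meta-analysis. The test-negative analysis, meant as a check on the cohort, would use a different case definition, so a disagreement between the two could come from the definition rather than from healthcare-seeking bias.

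**Working it through.** The protocol states no event count, power or combined VE that rests on this definition, so there is no figure of its own to reproduce. The calculations below are illustrations.

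**Inputs from the protocol (section 7).** Recent multi-site estimates for older adults are 28–37% for H1N1pdm09, 28–42% for H3N2 and 58–66% for B. A meta-analysis in older adults gives 24% for H3N2, 62% for H1N1pdm09 and 63% for B. The Danish 2015/16 register estimates at age 65 and over are 35.0% for H1N1pdm09 and 4.1% for B.

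**Assumptions not in the protocol.** f is the share of A-positives with a known subtype. p is the share of A among infections in the unvaccinated, set to 0.80. Events are treated as rare, so that risks of A and B add.

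**1. VE against A, subtyping unrelated to vaccination.** Both arms lose the same fraction of A events, so the risk ratio is unchanged and each absolute risk is multiplied by f. The SE of the log risk ratio is roughly √(1/e₁ + 1/e₀), where e₁ and e₀ are the event counts in the two arms. It therefore grows by 1/√f: 1.05 at f = 0.9, 1.41 at 0.5, 2.0 at 0.25 and 3.16 at 0.1.

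**2. VE against A, subtyping differing by vaccination status.** With subtyped shares s₁ (vaccinated) and s₀ (unvaccinated), apparent VE = 1 − (s₁/s₀)(1 − VE_A). Take a true VE_A of 43%, the midpoint of 24% and 62%:

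- s₀ = 0.30, s₁ = 0.25: 1 − 0.8333 × 0.57 = 52.5%.
- s₀ = 0.25, s₁ = 0.30: 1 − 1.2 × 0.57 = 31.6%.

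**3. Combined VE, if combined means either Table 4 row.** With f equal in both arms:

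VE = [p·f·VE_A + (1 − p)·VE_B] / [p·f + (1 − p)]

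B's share of counted events in the unvaccinated is (1 − p)/[p·f + (1 − p)].

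With VE_A 30% and VE_B 62%:

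- f = 1: 0.8 × 0.30 + 0.2 × 0.62 = 36.4%.
- f = 0.5: (0.12 + 0.124)/0.6 = 40.7%.
- f = 0.1: (0.024 + 0.124)/0.28 = 52.9%.

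The same formula for other inputs gives:

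| VE_A / VE_B | f = 1 | 0.9 | 0.5 | 0.25 | 0.1 |
|---|---|---|---|---|---|
| 30% / 62% | 36.4% | 37.0% | 40.7% | 46.0% | 52.9% |
| 35.0% / 4.1% (Danish 2015/16) | 28.8% | 28.3% | 24.7% | 19.6% | 12.9% |
| 62% / 63% (H1N1pdm09, meta-analysis) | 62.2% | 62.2% | 62.3% | 62.5% | 62.7% |
| B's share of counted events | 20.0% | 21.7% | 33.3% | 50.0% | 71.4% |

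B's share rises in every column with f below 1. The movement in VE has the sign of VE_B − VE_A and vanishes when the two are equal. It also depends on p: with 24% and 63% at f = 0.5, combined VE goes from 27.9% to 31.1% at 90:10 and from 43.5% to 50.0% at 50:50.

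**The case against.** The strongest reply is that the wording is loose and the authors meant a result typed as influenza A. The abstract speaks of types, and the contents listed in section 9.4 for the Danish and Swedish laboratory registers mention no subtype field, so a literal filter is hard to square with the data described. This is plausible and cannot be excluded. It does not remove the need for a change: section 9.6 has one set of scripts run in all three countries, and a script that followed Table 4 to the letter would drop valid cases.

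A second reply is that the combined outcome may mean any positive influenza test. Then the over-weighting of B disappears. The union of the two rows is the natural reading, since Table 4 offers nothing else, but the protocol does not say so. This stands as a condition on step 3 above.

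Third, the reach is limited. Hospitalisation and death are untouched, the prior-event-rate, regression-discontinuity and Day 0 analyses all concern influenza hospitalisation, and VE against A is distorted only if subtyping differs by vaccination status. That is correct.

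A reader might go further and infer that the combined VE is biased upward, because several figures in section 7 put VE against B above VE against A. The documents do not support that as a general statement. The Danish 2015/16 values in the same section give a downward shift, and the meta-analysis values for H1N1pdm09 and B give almost none. Nor do they support the inference that most A-positives lack a subtype: the larger shifts in the table need a low f, for which the protocol offers no evidence.

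**Conclusion.** The inconsistency is in the text and affects a primary outcome in all three countries. Applied as written, the definition excludes A-positives without a subtype, costs precision by about 1/√f, scales down absolute risks for A, and opens a route to bias in VE against A if subtyping differs by vaccination status. The over-weighting of B follows for any f below 1, provided that combined means either Table 4 row.

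The size is unknown, because neither f nor the A:B split is given. The effect starts at zero (f = 1, or equal VEs). At 80:20 and f = 0.5 it is about +4 points with 30% and 62%, and about −4 points with the Danish 2015/16 values. At f = 0.1 the same inputs give about +16 points each way in size, upward in the first case and downward in the second. The direction cannot be stated in advance.

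**What to change.** In Table 4, define laboratory-confirmed influenza A as any positive influenza A test, whether or not subtyped, in all three country rows. Add a definition of the combined outcome as any positive influenza A or B test. Use subtype for description only, and report the share of A-positives with a known subtype by country and vaccination status where the registers hold it. If typed as A was the intended meaning, the same edit corrects the wording.

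The cost is three table rows, one added line and one filter in the common scripts, with no extra data needed for the outcome. It should be done before the scripts are run for effectiveness results.

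### Table 5 counts an ARI/SARI admission only if the patient has not been discharged home, with no time point; read literally, this drops admissions that end at home and conflicts with Table 1

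*Protocol*

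**What the plan says.** Table 5 in section 9.3 defines ARI/SARI hospitalisation in the same words for Denmark, Finland and Sweden. Three conditions must all be met:

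- (a) on discharge status, the patient "has been admitted to hospital during the study period and has not been discharged to their home or home equivalent";
- (b) on length of stay, the patient was an inpatient or the contact lasted 12 hours or longer;
- (c) on cause, the main code lies in the range J09-J22.

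Table 1 in section 9.1 lists the same secondary outcome as "Hosp. due to ARI or SARI – J09-J22". The abstract calls it "hospitalisation for respiratory infections". Neither mentions discharge. The primary influenza hospitalisation outcome in Table 4 is "Defined as a hospitalization with a PCR positive test for influenza within 14 days before to 2 days after the admission date", with contact and code conditions and again nothing on discharge.

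For influenza-like illness, Table 5 takes codes "used as a primary or secondary diagnosis" in Denmark. The Finnish and Swedish rows read "Defined as ICD-10 diagnostic codes J09, J10 and J11 used as a primary diagnosis". None of the three rows requires a hospital stay, although Table 1 and the abstract's list of secondary outcomes describe hospitalisation for ILI.

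**The concern.** Condition (a) reads like a rule for counting patients who are in hospital at a given moment. Here it defines an incident event in a time-to-event analysis. An event should be settled when it happens; this one cannot be settled until the admission has ended, and then only by where the patient went.

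If the clause is programmed as written, vaccine effectiveness would be estimated against a mixture of in-hospital death, transfer elsewhere and unfinished stays. Section 9.8 and Table 8 warn that frailty, especially near the end of life, biases effectiveness upwards. A definition that gives deaths more weight moves the outcome in that direction. Because one set of scripts is run in every country (section 9.6), a literal filter would be carried into each country's result and then into the pooled one.

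**Working it through.** The protocol states no figure to reproduce. The check sets its definitions side by side and then adds an illustration of size.

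**1. Is the clause a required condition?** Yes. It stands inside (a), and (a), (b) and (c) are joined by *and*. No row says when discharge status is assessed, and no other section explains or qualifies it.

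**2. Can it be applied literally?** Table 7 (section 9.4) says that the Finnish Care Register and the Swedish inpatient register both hold discharge destination, including the patient's own residence. So it can be applied in those two countries. The Danish register description mentions contact duration, department and other hospital characteristics, but not destination. The effect in Denmark therefore depends on how the clause is coded.

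**3. Does it fit the analysis?** Section 9.7 follows each person until the day of an outcome event, death, emigration or end of study. Under (a), status on the admission day depends on later information. A patient still in hospital at data extraction qualifies on (a); the same patient, sent home a week later and extracted after that, does not. Section 9.9 expects near-real-time data from Denmark and Finland but a single, later delivery from Sweden, so the rule could act differently by country for administrative reasons.

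**4. Are the conditions compatible?** Table 7 describes the Finnish and Swedish codes as discharge diagnoses. A patient still admitted may not yet have the J09-J22 code that (c) demands. In those countries (a) and (c) pull against each other.

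**5. How much precision could be lost?** The share of admissions discharged home, *h*, is not in the protocol. Assume 50% to 90%. The share of events kept is 1 − *h*. With rare events and the same share kept in both groups, the standard error of the log risk ratio scales as 1/√(1 − *h*).

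| Discharged home, *h* (assumption) | Events kept | SE multiplier |
|---|---|---|
| 50% | 50% | 1/√0.50 = 1.4 |
| 75% | 25% | 1/√0.25 = 2.0 |
| 90% | 10% | 1/√0.10 = 3.2 |

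**6. ILI.** The diagnosis position differs between Denmark and the other two countries. The note under Table 6 that defends country-specific codes concerns comorbidities, not outcomes. The Danish register covers all hospital contacts and visits, and the Finnish and Swedish registers include outpatient specialist care. As Table 5 stands, contacts without admission could count as ILI events, contrary to Table 1.

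**The case against.** The strongest reply is that the clause was never meant to remove recovered patients. It may describe someone admitted rather than sent home, someone currently in hospital, or a rule for joining transfers into one admission. The row title, Table 1 and the abstract all point to ordinary hospitalisation. Table 1 is also shorthand: for influenza hospitalisation it omits the test window and the contact-length rule, so its silence on discharge is weak evidence alone.

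Much of this stands as an account of how the wording may have arisen. It does not make the wording usable, because the protocol states none of these purposes and a programmer would have to guess. Two of the readings need no discharge clause: the inpatient-or-12-hours condition already deals with contacts sent straight home, and a first-admission rule with transfers joined deals with transfers. A current-inpatient count does not suit an incident outcome.

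A reader might infer that the analysis will lose most of its ARI/SARI events. The protocol does not support that: it gives no discharge-home share, and at 50% only half are lost. Nor does it establish that the clause will act identically in all three countries, or that transferred patients are frailer; section 9.8 discusses frailty and end of life, not transfer.

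On ILI, it is fair to say that the difference in diagnosis position is openly stated, that country estimates are reported separately and that pooling uses random effects. Random effects allow for heterogeneity between countries; they do not make two outcome definitions into one.

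**Conclusion.** The ARI/SARI definition in Table 5 is unsound as written. It contains a mandatory, undated discharge condition which, taken literally, excludes admissions ending at home, ties event status to post-admission course and extraction date, and disagrees with Table 1 and the abstract. That conclusion rests on the text alone.

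The size does not. A loss of 50% to 90% of events, with a standard error 1.4 to 3.2 times larger, holds only under the assumed discharge-home share and literal application. The text supports literal application as feasible in Finland and Sweden and leaves it open in Denmark.

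It would go too far to treat this as a threat to the main results. The affected outcomes, ARI/SARI and ILI, are secondary. The primary outcomes carry no discharge clause, and the PERR, regression discontinuity and day-0 analyses use influenza hospitalisation. This should be fixed before the scripts are run; it is not a critical defect. The ILI inconsistency is real but separate, and its size cannot be derived from the protocol.

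**What to change.** - **ARI/SARI, Table 5, all three rows:** delete the clause on discharge home. Define the event as the first admission during follow-up, inpatient or at least 12 hours, with a primary J09-J22 code, dated at admission. State that an onward transfer is part of the same admission.
- **ILI, Table 5:** choose one diagnosis-position rule (primary only, or primary and secondary) and use it in all countries before pooling. State the hospitalisation requirement so that Table 5 matches Table 1.

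The cost is a wording change and a simpler filter in the common scripts. No further data are needed.
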